## APPENDIX 3: HRQOL QUESTIONNAIRES

### Recoding and Scales

Before calculating the scale and total scores several items need to be reverse scored (Table\_App3.01, Table\_App3.02). The reverse scoring for those items is as follows: (1=5), (2=4), (3=3), (4=2), and (5=1). Any (0) will be recoded as missing data for the purposes of scale scoring. In listings of frequencies, the number of patients reporting 'Not applicable' can also be displayed.

After the recoding the 3 scores can be calculated as follows:

1. **Raw Scale Score:** Derived as the sum of all items in a scale. , e.g. the raw score for physical health is the sum of the 5 items from this scale. A Total score is calculated by summing up all of the raw and reverse coded items in the available scales.
2. **Standardized Scale Score:** The raw scale score is divided by the number of items in the scale. That way a comparison of scores across scales per patient is possible.
3. **Transformed Scale Score:** The scores for each scale can be standardized onto a 100 point scale. This is done with the following formula:

$$TSC = 100 \times \frac{(\text{raw scale score} - \text{minimal possible raw score})}{\text{possible range of raw scale scores}}$$
$$= 100 \times \frac{(\text{standardized scale score} - 1)}{4}$$

The transformed Scale Score will be used for all analyses and referred as domain score or total score on the outputs.

Table\_App3.01: The questions from Haem-A-QoL whose items need recoding are:

Category	Question
View of yourself	I felt comfortable with my body
	I was able not to think all the time about my hemophilia
Dealing with hemophilia	I tried to recognize early on when a bleed developed
	I was able to tell whether or not I was bleeding
	I was able to control my bleeds
Treatment	I was satisfied with the hemophilia center
Future	I have been expecting that things will get better in the future
Sports and leisure	I played sports just as much as others

Work and school	I was able to go to work/school regularly in spite of my hemophilia
	I was able to work/study like healthy colleagues

Table\_App3.02: The questions from Haemo-QoL-SF whose items need recoding are:

Category	Question
View of yourself	I felt as well as other boys my age
	I felt contented about my body
Friends	My best friend cared about how I was feeling
	There was a best friend that I felt very close to
	My friends took care of me when I felt bad
Sports and school	I did as much sports as any other kid
Dealing with hemophilia	I was in control of my complaints due to haemophilia
	Haemophilia was a normal part of my life
	I felt healthy in spite of my haemophilia
	I accepted having haemophilia
Treatment	The treatment I got was okay

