## Missing items

Scales can be calculated if > 50% of the items have been answered. As the questionnaire is being administered electronically and patients are not able to skip items, there should not be any missing items. However, as patients can answer “Not applicable” to questions in the sports and leisure, work and school, and family planning scales, items could be treated as missing. In this case, the minimum number of items that needs to be completed and not responded to as “Not applicable” is:

- Sports and leisure: 3
- Work and school: 2
- Family planning: 2

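### SAP Appendix 3 sets 'not applicable' to missing but divides by all items in the scale, so as written a partly answered Haem-A-QoL scale is scored too low and can fall below 0

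*SAP*

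**What the plan says.** SAP Appendix 3 (Recoding and Scales) builds the Haem-A-QoL and Haemo-QoL-SF scores in three steps, after this recoding: "Any (0) will be recoded as missing data for the purposes of scale scoring". The code 0 stands for 'not applicable'.

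- **Raw score:** the sum of the items in a scale. The total is handled separately: "A Total score is calculated by summing up all of the raw and reverse coded items in the available scales".
- **Standardized score:** "The raw scale score is divided by the number of items in the scale". The stated purpose is: "That way a comparison of scores across scales per patient is possible".
- **Transformed score:** "The scores for each scale can be standardized onto a 100 point scale". Two formulas are printed with an equals sign between them. One subtracts the lowest possible raw score and divides by the possible range. The other is 100 × (standardized score − 1)/4. This score is the one used in all analyses, for domains and for the total.

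The Missing items part of the same appendix gives a general rule, "Scales can be calculated if > 50% of the items have been answered". For the three scales that offer 'not applicable', it then lists "the minimum number of items that needs to be completed and not responded to as" 'not applicable': 3 for sports and leisure, 2 for work and school, 2 for family planning.

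No section states a divisor based on answered items. SAP 4.6.2 only refers to Appendix 3, and the missing-data rules in SAP 4.11 deal with bleeds and their treatment.

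**The concern.** An item set to missing adds nothing to the sum but still counts in the stated divisor. Each unanswered item then pulls the score down as if it had been rated below the best possible answer. The protocol (section 1.2.2.3, footnote to the Haem-A-QoL table) says that lower scores mean better functioning. The error therefore makes the affected scale look better at that visit, and it can push the score off the 0 to 100 range.

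For change from baseline, two things can happen. If the same items are 'not applicable' at both visits, the change is shrunk. If the pattern differs between visits, a false change appears, in either direction. SAP 4.6.2 applies paired t-tests to the change in these scales at 6 months and uses responder thresholds of 7 points (Haem-A-QoL total) and 10 points (physical health).

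**Working it through.** **Inputs.** Items are coded 1 to 5, with 0 set to missing (SAP Appendix 3). Minimum answered items are 3, 2 and 2 (same appendix). Physical health has five items: "the raw score for physical health is the sum of the 5 items from this scale". The current text does not give item counts for the three 'not applicable' scales. The superseded US form, printed as deleted material in the protocol's summary of changes, has 5, 4 and 4. Its ten scales give 5+4+5+5+4+3+8+5+4+3 = 46, matching the 46 items in SAP 2.2.3. I treat 5/4/4 as an assumption and show smaller counts beside it.

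**Complete scale (reproduces the SAP).** With all n items answered, the minimum is n and the range is 4n. The first formula is 100 × (raw − n)/(4n) and the second is 100 × (raw/n − 1)/4. They are identical and run from 0 to 100. For n = 5 and raw = 15, both give 50.

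**Partly answered scale.** Let k of n items be answered with mean m.

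- As stated: 100 × (k·m/n − 1)/4 = 25 × (k·m/n − 1).
- Divisor equal to answered items: 25 × (m − 1).
- Shortfall: 25 × m × (1 − k/n), positive whenever k < n.
- At m = 1 the stated rule gives 25 × (k/n − 1), which is negative for every n > k. This needs no item count.

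| Answered | k/n | As stated, all 1 (should be 0) | As stated, all 3 (should be 50) |
|---|---|---|---|
| 2 of 3 | 0.67 | −8.3 | 25 |
| 2 of 4 | 0.50 | −12.5 | 12.5 |
| 3 of 4 | 0.75 | −6.25 | 31.25 |
| 3 of 5 | 0.60 | −10 | 20 |

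**The two printed formulas.** Take 2 of 4 items answered, both 3, so raw = 6. The first formula over the answered items gives 100 × (6 − 2)/8 = 50. Over all items it gives 100 × (6 − 4)/16 = 12.5. The second formula with the stated divisor gives 100 × (6/4 − 1)/4 = 12.5. The equals sign holds only if both sides use the same item set, and the appendix does not say which.

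**Comparison across scales.** A patient answering 3 throughout has a standardized score of 3.0 on a complete scale. With two of four items 'not applicable', it is 6/4 = 1.5.

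**Change from baseline.** If the pattern is stable, change is multiplied by k/n: 50% to 75% of its true size in the cases above, and 80% with one of five missing. If the pattern changes, a four-item scale answered 3 throughout moves from 12.5 (two 'not applicable') to 50 (none) with no real change. The reverse order shows a false improvement of the same size.

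**Blank items on paper.** SAP 2.2.3 allows paper forms when the device is unavailable. For physical health with one item blank, mean 2 gives 100 × (8/5 − 1)/4 = 15 instead of 25, and mean 3 gives 100 × (12/5 − 1)/4 = 35 instead of 50. If the blank occurs at only one of the two visits, this 10- to 15-point shift meets or exceeds the 10-point threshold.

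**Total score.** No divisor, minimum or range is stated for a sum over the scales that happen to be available, so the effect cannot be sized from the text. As an illustration only: if the divisor were 46, with six 'not applicable' answers and all others 3, the score would be 100 × (120/46 − 1)/4 = 40.2 instead of 50.

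**The case against.** The strongest reply is that the low scores come from a mixed reading. If 'not applicable' is missing rather than zero, a sum over all items is undefined. One must first sum the answered items only, and a consistent reader would then divide by the same items. The 100-point range, the comparison across scales and the minimum-answered rule all point to a mean of answered items. The scoring program, or the instrument publications the SAP cites, may already settle the matter, and neither is available here.

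The reply is right about intent: a mean of answered items was probably meant, and nothing shows that the program is wrong. It does not rescue the text. The Missing items rule requires a score when items are missing, so the sum must run over answered items, while the divisor is stated in words as the items in the scale. A programmer who follows those words gets off-scale values.

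Some limits on size also stand. The 5/4/4 counts are assumed. With four items, 2 of 4 is exactly 50% and would fail the general rule of more than 50%; under that stricter rule the stated scores still reach −6.25 (3 of 4) and −10 (3 of 5). Blank items can arise only on paper forms.

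**Conclusion.** The concern holds. The stated divisor gives scores that are too low by 25 × m × (1 − k/n) on any partly answered scale, below 0 when every answered item has the best rating, and inconsistent with the SAP's own pair of formulas. The sign and the formula do not depend on item counts. The sizes at the stated minimums do: 12.5 to 31.25 instead of 50, over assumed scale lengths of 3 to 5 items.

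The documents give no frequency of 'not applicable' answers or of paper forms, so the net direction of the effect on change from baseline is unknown. None of the three 'not applicable' scales has its own responder threshold. Responder proportions are reached only through the total score or through a blank item on a paper form. SAP section 4 declares all analyses descriptive, these outputs are secondary, and the safety and bleed endpoints are untouched. The severity is minor. Confidence in the finding about the text is high.

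**What to change.** In SAP Appendix 3:

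- Define the standardized score as the sum of the answered items divided by the number of answered items, and take the minimum and range over those same items. The two printed formulas then agree, and every score that is calculated lies between 0 and 100.
- Apply the same rule to the total score, over the answered items in the scales that can be scored, and to items left blank on paper forms.
- Keep more than 50% answered as the general rule, and label the minimums of 3, 2 and 2 as the specific rule for the three 'not applicable' scales, so that 2 of 4 is not left in doubt.

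The cost is one or two sentences in the appendix and one line in the scoring program. No new data are needed.

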## Missing items

Scales can be calculated if > 50% of the items have been answered. As the questionnaire is being administered electronically and patients are not able to skip items, there should not be any missing items. However, as patients can answer “Not applicable” to questions in the sports and leisure, work and school, and family planning scales, items could be treated as missing. In this case, the minimum number of items that needs to be completed and not responded to as “Not applicable” is:

- Sports and leisure: 3
- Work and school: 2
- Family planning: 2
